7.21.3 Procedures for Recording and Reporting Adverse Events

7.21.3.1 Reporting Serious Adverse Events

Any SAE, regardless of relationship to study medication, which occurs in a patient after informed consent, should be recorded by the clinical site on an SAE form. The SAE must be completely described on the patient's eCRF, including the judgment of the Investigator as to the relationship of the SAE to the study drug or device. The Investigator will promptly supply all information identified and requested by the Sponsor (or contract research organization [CRO]) regarding the SAE.

The Investigator must report the SAE to the Shire Pharmacovigilance and Risk Management Department AND to the Shire HGT Medical Monitor on an SAE form. This form must be completed and FAXED within 24 hours of the Investigator's learning of the event to:

Shire Pharmacovigilance and Risk Management Department:

International FAX: [REDACTED] (UK) OR **United States FAX:** [REDACTED]

AND

Shire HGT Medical Monitor: [REDACTED] MD

[REDACTED]
FAX: [REDACTED] (USA)

Any follow-up information must also be completed on an SAE form and faxed to the same numbers listed above.

In the event of a severe and unexpected, fatal, or life-threatening SAE, the clinical site must contact the Shire HGT Medical Monitor by telephone; this is in addition to completing and transmitting the SAE form as stated above. The following provides contact information for the Shire HGT Medical Monitor.

If an SAE is assessed as severe and unexpected, or life-threatening, contact:

[REDACTED] MD
[REDACTED]
Shire Human Genetic Therapies, Inc.
[name]
[name]
Telephone: [REDACTED]
Fax: [REDACTED] (USA)
Mobile: [REDACTED]

The Investigator must promptly report all required information to the Institutional Review Board (IRB)/ Independent Ethics Committee (IEC). It is the responsibility of the Sponsor to ensure that each Investigator receives a copy of any CIOMS I/ MedWatch report that has been submitted to the appropriate regulatory agencies notifying them of an unexpected related SAE. The Investigator or Sponsor must ensure that the IRB/IEC receives a copy of the report and that a copy is also filed within their study files.

7.21.3.2 Eliciting Adverse Events

Patients should be asked non-leading questions (eg, “How do you feel?”) and further questions should be posed if there is indication of an AE. The questioning should be conducted with due regard for objectivity and, in particular, the questioner should gather information regarding AEs from questioning the patient, the patient’s parent/guardian, spontaneous report by the patient or parent/guardian, laboratory reports, and any health care provider’s observations.

The onset date, resolution date, treatment administered, and outcome of each AE must be recorded on the appropriate eCRF. In addition, the relationship of each AE to study medication must be recorded.

7.21.3.3 Protocol Deviations for Medical Emergency or Adverse Event

During and following a patient’s participation in the study, the Investigator should ensure that adequate medical care is provided to a patient for any AEs, including clinically significant laboratory test results. The Investigator should inform the patient, the patient’s parent(s), or the patient’s legally authorized representative when medical care is needed for intercurrent illness(es) of which the Investigator becomes aware. In an emergency situation, the Investigator should contact the Shire HGT Medical Monitor (see [Section 7.21.3.1](#)).

Only when an emergency occurs that requires an immediate deviation from the protocol for the safety of a patient, will there be such a deviation and this will be only for that patient. The Investigator or other physician in attendance in such an emergency must contact the Shire HGT Medical Monitor as soon as possible.

The Investigator, along with the Shire HGT Medical Monitor, will make a decision as to whether or not the patient should continue in the study prior to the next scheduled dose. The departure from the protocol and the grounds for it should be stated in the eCRF.

7.22 Pregnancy

Pregnancy and lactation are exclusion criteria. The Sponsor must be notified in the event of a pregnancy occurring during the course of the study and through 30 days after the patient's last dose of study drug. Pregnancy is not to be reported as an AE; the pregnancy reporting form should be used to report the pregnancy. The pregnancy will be followed up through delivery or final outcome.

7.23 Removal of Subjects from the Trial or Study Drug

The patient's parent or legal guardian acting on behalf of the patient is free to withdraw consent and discontinue participation in the study at any time without prejudice to further treatment. Since this is an extension trial, there will be no replacement of patients who discontinue the study for any reason.

A patient's participation in the study may be discontinued at any time at the discretion of the Investigator, Sponsor or Medical Monitor. The following may be justifiable reasons for the Investigator, Sponsor or Medical Monitor to remove a patient from the study:

- Adverse Event: If a patient experiences an AE which, in the judgment of the investigator, the sponsor, or the medical monitor, presents an unacceptable consequence or risk to the patient.
- Adverse Laboratory Experience: If a patient has an adverse laboratory experience which, in the judgment of the investigator, the Sponsor, or the medical monitor, presents an unacceptable consequence or risk to the patient, the patient may be withdrawn from the study.
- Comorbidity: If a patient develops comorbidity during the course of the study that is independent of the study indication, and treatment is required that is not consistent with protocol requirements.
- Intercurrent Illness: If a patient develops an illness during the course of the study that is not associated with the condition under study, and which requires treatment that is not consistent with protocol requirements.
- Refusal of Treatment: If for any reason the patient refuses treatment during the study, the patient will be withdrawn from the study, and the reason for refusal will be documented on the eCRF. Reasonable efforts will be made to monitor the patient for AEs following such discontinuation. Such efforts will be documented in the eCRF.
- Withdrawal of Informed Consent: A patient's parent or legally authorized guardian may withdraw his informed consent to participate in the study at any time.
- Cerebrospinal fluid leukocyte count >100 cells per cubic millimeter for 2 consecutive months.
- New onset seizure.
- Anaphylactic reaction beyond reasonable management as described in the Investigator's Brochure.

- Clinically problematic intubations or extubations which may preclude safe airway management and anesthesia.
- Development of refractory spinal fluid leakage.
- Clinically significant prolonged (eg greater than 24 to 48 hours) worsening in mental status, including development of new focal or non-focal neurological symptoms, or recurrence of a previously stable prior medical problem judged due to study drug or participation that is exclusive of effects from anesthesia.
- Non-compliance, including failure to appear at 1 or more study visits.
- The patient was erroneously included in the study.
- The patient develops an exclusion criterion.
- The study is terminated by the Sponsor.

If a patient or the patient's legal guardian(s), acting on behalf of the patient, discontinues participation in the study, or the patient is discontinued by the Investigator, the Patient Completion/Discontinuation Case Report Form (eCRF) describing the reason for discontinuation must be completed. Any adverse events (AE's) experienced up to the point of discontinuation must be documented on the AE eCRF. If AEs are present when the patient withdraws from the study, the patient will be re-evaluated within 30 days of withdrawal. All ongoing SAEs at the time of withdrawal will be followed until resolution.

At the time of discontinuation or withdrawal, patients will be asked to participate in all safety and efficacy evaluations required for the end of study visit and for the safety follow-up visit. Participation in these EOS procedures will be strongly encouraged, but is voluntary for those patients electing to discontinue from the study. The patient will be scheduled for the removal of the IDDD.

7.24 Other Study Procedures

This section is not applicable.

7.25 Appropriateness of Measurements

The neurocognitive and developmental assessments are intended to gauge which domains can be accurately measured, with which specific tools, despite the considerable behavioral and cognitive challenges in Sanfilippo syndrome. The evaluation of these domains and the analysis of CSF, serum, and urine biomarkers will provide the pivotal data necessary to inform the clinical assessments and biomarkers used in possible future Sanfilippo syndrome ERT trials.

8 STUDY ACTIVITIES

Patients who participated in Study HGT-SAN-055 through Week 26 (patients who were dosed monthly) or Week 28 (patients who were dosed every other week) and completed the End of Study evaluations will be eligible for enrollment in this open-label extension study. Informed consent will be provided by the patient's parent(s)/legal guardian(s) prior to start of extension study procedures.

If there are no safety concerns, patients who were previously treated with intrathecal rhHNS in Study HGT-SAN-055 and elect to continue rhHNS treatment will continue receiving monthly (Groups 1 and 2) or EOW (Group 3) intrathecal rhHNS in this extension study, as described in [Appendix 1](#) Schedule of Events.

8.1 Screening Visit/Baseline Visit

All Screening assessments for this study are to have been performed during the Week 26 (Groups 1 and 2) or Week 28 (Group 3) (30 [\pm 7] days after the last rhHNS administration) EOS procedures in HGT-SAN-055. If less than 60 days have elapsed since completion of the EOS assessments for HGT-SAN-055, the assessments detailed in this Screening visit are not required to be repeated. The Baseline Visit for this study will be the first day the patient received his/her IT dose of rhHNS in Study HGT-SAN-055.

If more than 60 days have elapsed following the HGT-SAN-055 EOS procedures, patients will be evaluated for enrollment in HGT-SAN-067 on a case-by-case basis by the Investigator. A decision about enrollment will be made following discussion with the Medical Monitor. If the patient is enrolled, the following assessments are to be repeated within 30 days prior to the first scheduled intrathecal rhHNS dose:

- Physical examination
- Height and weight
- Head circumference
- ECG
- Vital signs
- Hematology
- Serum chemistry
- Urinalysis
- Neurological examination (performed prior to the administration of anesthesia)
- Neurodevelopmental assessments (performed prior to the administration of anesthesia)
- General anesthesia: administration of anesthesia will be given prior to the following assessments:
 - ABR
 - MRI of the head
- CSF sample collection (chemistry, cell count, heparan sulfate and heparan sulfate derivatives, and other MPS exploratory biomarkers) via the IDDD
- Urine heparan sulfate and heparan sulfate derivatives

- Serum heparan sulfate and heparan sulfate derivatives
- Anti-rhHNS antibody testing
- Children's Sleep Habits Rating Scale
- CHQ-50
- CHQ-87
- ITQOL
- Concomitant medications, therapies, and procedures
- AE assessments

8.2 Treatment: Monthly, Weekly Assessments

Patients in Dose Groups 1 and 2 will receive rhHNS IDDD monthly, on Week 1, Day 2 (± 2 days). Patients in dose Group 3 will receive rhHNS EOW, on Weeks 1 and 3, Day 2 (± 2 days).

8.2.1 Week 1 (Groups 1 and 2); Week 1 and 3 (Group 3)

8.2.1.1 Day 1 (Pre-treatment) Assessments

- Informed consent (Week 1, Month 1 only) prior to study HGT-SAN-067 study procedures
- Physical examination
- Height and weight
- Vital signs
- Hematology
- Serum Chemistry
- Urinalysis
- Neurological Examination (performed prior to the administration of anesthesia and the rhHNS IT injection)
- Concomitant Medications, Therapies, and Procedures
- AE assessments

Note: If the HGT-SAN-055 EOS (or Screening) assessments were performed within 7 days of first intrathecal rhHNS treatment in this study, the pre-treatment assessments described in this section do not need to be completed prior to the first treatment

DAY 1 (PRE-TREATMENT) ADDITIONAL ASSESSMENTS PERFORMED ONLY AT MONTHS 12, 24, 36, AND 48

- Head circumference
- Visual and hearing assessments
- Urine Heparan Sulfate and Heparan Sulfate Derivatives (Group 3: obtained only at first week of each treatment month)
- Serum Heparan Sulfate and Heparan Sulfate Derivatives (Group 3: obtained only at first week of each treatment month)

- Anti-rhHNS antibody testing
- Auditory Brainstem Response (ABR)
- MRI of the head
- Full neurodevelopmental testing (performed prior to the administration of anesthesia and the rhHNS IT injection)
- Children's Sleep Habits Rating Scale
- Child health questionnaire-50
- Child health questionnaire-87
- Infant toddler QOL Questionnaire

8.2.1.2 Day 2 (± 2 days) Assessments and IDDD Injection of rhHNS

- Physical examination
- ECG (performed following IT study drug injection)
- Vital signs
- CSF sample collection (obtained prior to IT study drug injection)
- rhHNS IT injection (Day 2 ± 2 days)
- neurological examination
- Concomitant medications, therapies, and procedures
- AE assessments

8.2.1.3 Day 3 (Post IT Dose) Assessments

Patients will be discharged when deemed clinically stable by the Investigator.

- Vital signs
- Neurological examination
- Concomitant medications, therapies, and procedures
- AE assessments

8.3 End of Study/ Early Termination Procedures

Patients who complete the study or who discontinue prior to the end of the study, will have EOS assessments performed 30 (± 7 days) after their last dose of rhHNS. Patients who discontinue or are withdrawn prior to study completion will be asked to participate in the end of study procedures at time of discontinuation. Participation in these EOS procedures will be strongly encouraged, but is voluntary for those patients electing to discontinue from the study. Note: scheduled removal of the IDDD will be required at study completion with sedation or anesthesia, as required.

- Physical examination
- Height and weight
- Head circumference
- Visual and hearing

- ECG
- Vital signs
- Hematology
- Serum Chemistries
- Urinalysis
- Urine Heparan Sulfate and Heparan Sulfate Derivatives
- Serum Heparan Sulfate and Heparan Sulfate Derivatives
- Anti-rhHNS antibody testing
- Auditory Brainstem Response (ABR)
- MRI of the head
- CSF sample collection
- Neurological examination
- Full neurodevelopmental testing
- Children's Sleep Habits Rating Scale
- Child health questionnaire-50
- Child health questionnaire-87
- Infant toddler QOL Questionnaire
- Concomitant medications, therapies, and procedures
- AE assessments

8.4 Safety Follow-up Visit (by Telephone)

Patients who complete the study will have a safety follow-up visit 30 Days (± 7 days)

Patients who discontinue or are withdrawn prior to study completion will be asked to participate in the safety follow-up visit at the time of discontinuation. Participation in these procedures will be strongly encouraged, but is voluntary for those patients electing to discontinue from the study.

- Concomitant medications, therapies, and procedures
- AE assessments

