Patients whose parents/legal guardians provide written informed consent/assent to participate in this study will check in with the study center 1 day prior to rhHNS dosing for safety assessments on each rhHNS treatment week. If no safety concerns exist, the patient will subsequently receive IT administration of rhHNS on Day 2 (± 2 days). Patients will be discharged from the inpatient unit a minimum of 1 day following dosing with rhHNS and when deemed clinically stable by the Investigator.

The patient will have already received a standardized battery of neurodevelopmental assessments at the Baseline and 6-month time points in the HGT-SAN-055 study. These same assessments and tests will be performed at 12, 24, 36, and 48 months. Similarly, MRI of the head, ABR testing, CSF sampling by means of lumbar puncture and any other procedures requiring anesthesia will be performed at 12, 24, 36, and 48 months.

All patients will undergo end of study procedures 30 (\pm 7) days following their last administration of rhHNS. End of study procedures will include a standard battery of clinical laboratory tests (serum chemistry, hematology, and urinalysis) in CSF and blood, protocol specific laboratory testing (eg, anti-rhHNS antibody testing), neurodevelopmental testing, ABR, child health questionnaires, MRI, and concomitant medications and AE monitoring.

All patients will be contacted by telephone for a Final Safety Follow-up, to be conducted at 30 (\pm 7) days after the EOS procedures to collect updated information on adverse events and concomitant medications, therapies, and procedures.

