7.21 Adverse Events

7.21.1 Adverse Events Assessments

Adverse events will be monitored continuously throughout the study from the time the patient, patient's parent/legal guardian signs the informed consent/assent (if applicable) until the safety follow-up contact or until the event has resolved or stabilized, or an outcome is reached, whichever comes first.

If the Investigator considers it necessary to report an AE in a study patient after the end of the observation period, he or she should contact the Sponsor to determine how the AE should be documented and reported.

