10.6 Efficacy, Safety, and Pharmacodynamic Evaluations

10.6.1 Primary Analyses

10.6.1.1 Safety Analysis

In general, safety assessments will be based on all assessments post-baseline. The assessment of safety will be based primarily on the frequency of treatment-emergent adverse events, due to study drug and on the frequency of clinically notable abnormal vital sign and laboratory values. Changes from baseline will be calculated by subtracting the baseline value from the post-baseline value.

All enrolled patients will be included in the safety analysis. Patients will be grouped according to the actual dose received.

No formal statistical test will be performed in the safety evaluations. Vital sign measurements, clinical chemistry, and hematology safety monitoring will be listed for each patient, and abnormal values will be flagged. These will also be summarized at each time point, including change from baseline.

Adverse events will be recorded throughout the study and at early termination. Adverse events and medical conditions will be coded using the Medical Dictionary for Regulatory Activities (MedDRA) Version 9.0 or later. In all cases (with the exception of device-related events), adverse event summaries will be based on all adverse event recorded beginning on Study Day 1 (treatment-emergent AEs).

Adverse events will be summarized by presenting, for each treatment group, the number and percentage of patients having any adverse event, having an adverse event in system organ class, and having each individual adverse event. Note that in any given category (eg, system organ class) a patient will only be counted once. In addition, those events which resulted in death or were otherwise classified as serious will be presented in a separate listing. The incidence of treatment-emergent adverse events (new or worsened from baseline) will be summarized by system organ class, severity, type of adverse event and relationship to trial medication.

Adverse events that occur up to 30 days after the last dose of study drug will be considered “on-treatment”. Adverse events which are deemed probably or possibly related to the device will be summarized by dose group and overall.

Laboratory data will be listed by patient and dose group. Patients with newly occurring abnormalities outside the normal range will be flagged and listed separately and summarized. Mean change from baseline values or shift tables will also be provided by dose group at each visit.

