^f All patients who complete the study will have end of study assessments performed 30 (±7 days) after their last dose of study drug.

^g If a patient’s IDDD becomes nonfunctional or infected; it will be replaced so that the patient can remain on study. See [Section 6.5](#).

^h A safety follow up telephone call will be made 30 (±7 days) after End of Study Procedures.

ⁱ Assessments will be required only if more than 60 days have elapsed following the HGT-SAN-055 procedures. These assessments would be repeated within 30 days prior to the first scheduled rhHNS IT dose.

^j Blood sample drawn before IT injection of rhHNS.

^k CSF will be tested for standard chemistries, heparan sulfate and heparan sulfate derivatives, anti-rhHNS antibodies, and MPS exploratory biomarkers.

Table 2 Study Assessments for Patients Who Have Received 6 Months of Treatment With rhHNS (Study HGT-SAN-055) (Dose Group 3)

Assessment	Screening/Baseline Visit ⁱ	Week 1 and 3 Each Treatment Month			12, 24, 36, and 48 months	End of Study ^f	Safety Follow-up ^h
		Pre-Tx Day 1 ^a	IT administration Day 2	Day 3 ^d			
Informed Consent/Enrollment		•					
Physical Examination	•	•	•			•	
Height and Weight	•	•				•	
Head Circumference	•				•	•	
Visual and Hearing Assessment					•	•	
ECG	•		• ^b			•	
Vital Signs	•	•	•	•		•	
Hematology	•	•				•	
Serum Chemistry	•	•				•	
Urinalysis	•	•				•	
Urine Heparan Sulfate and Heparan Sulfate Derivatives	•				• ^c	•	
Serum Heparan Sulfate and Heparan Sulfate Derivatives	•				• ^c	•	
Anti-rhHNS antibody testing (serum and CSF) ^j	•				•	•	
Auditory Brainstem Response (ABR)	•				•	•	
MRI of the Head	•				•	•	
CSF Sample Collection ^k	•		• ^c			• ^c	
rhHNS administration ^g			•				
Neurological Examination	•	•	•	• ^j		•	
Full Neurodevelopmental Testing	•				•	•	
Children's Sleep Habits Rating Scale	•				•	•	
Child Health Questionnaire-50	•				•	•	
Child Health Questionnaire-87	•				•	•	
Infant Toddler QOL Questionnaire	•				•	•	

Table 2 Study Assessments for Patients Who Have Received 6 Months of Treatment With rhHNS (Study HGT-SAN-055) (Dose Group 3)

Assessment	Screening/Baseline Visit ⁱ	Week 1 and 3 Each Treatment Month			12, 24, 36, and 48 months	End of Study ^f	Safety Follow-up ^h
		Pre-Tx Day 1 ^a	IT administration Day 2	Day 3 ^d			
Concomitant Medications, Therapies, and Procedures	•	•	•	•		•	•
Adverse Event Monitoring	•	•	•	•		•	•

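### For patients who stop early, the protocol contradicts itself on when adverse event collection ends, and one reading leaves no planned contact after device removal

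*Protocol*

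**What the plan says.** The timing of the last safety contact is stated in several places.

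- Section 4.1 (and the Synopsis): "All patients will be contacted by telephone for a Final Safety Follow-up, to be conducted at 30" (±7) days after the EOS procedures. No subgroup is excepted.
- Appendix 1, footnote h: "A safety follow up telephone call will be made 30 (±7 days) after End of Study Procedures". It is not limited to completers.
- Section 8.4, completers: "Patients who complete the study will have a safety follow-up visit 30 Days" (±7 days), with no reference point given.
- Section 8.4, early stoppers: "Patients who discontinue or are withdrawn prior to study completion will be asked to participate in the safety follow-up visit at the time of discontinuation".

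The timing of EOS for early stoppers is given twice in Section 8.3. The first sentence sets 30 (±7) days after the last dose for completers and early stoppers alike. The next says: "Patients who discontinue or are withdrawn prior to study completion will be asked to participate in the end of study procedures at time of discontinuation".

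The end of AE collection depends on that contact. Under Section 7.21.1, AEs are monitored "until the safety follow-up contact or until the event has resolved or stabilized, or an outcome is reached, whichever comes first". Section 7.23 asks for AEs up to the point of discontinuation to be documented and then adds: "The patient will be scheduled for the removal of the IDDD". Section 4.1 treats removal of the device after discontinuation as part of the EOS procedures. Section 7.23 also has AEs present at withdrawal re-evaluated within 30 days, and ongoing SAEs followed until they resolve.

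**The concern.** The primary endpoint is long-term safety, measured first by AEs, and the primary objective concerns patients treated through a surgically implanted device. The protocol lists infection, cerebrospinal fluid leakage, meningitis and nerve injury among the hazards of the device and of intraspinal access. The reasons for removing a patient in Section 7.23 include AEs, new seizures and refractory spinal fluid leakage, so some early stoppers will leave for safety reasons.

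If their last planned contact falls on the day they stop, with removal surgery still to come, the period after that surgery has no scheduled AE enquiry. Completers do have one. The difference in follow-up would then depend on why and when a patient left. An event never collected cannot be restored by any later analysis plan.

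**Working it through.** There is no sample size or power figure to reproduce. The check is day arithmetic, with the last dose as day 0.

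**Inputs.** EOS at 30 ± 7 days after the last dose (8.3, first sentence). EOS at discontinuation (8.3, second sentence). Contact 30 ± 7 days after EOS (4.1, Appendix 1). Contact at discontinuation (8.4). Maximum 12 patients (5.1, 10.2).

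**Completers.**
- EOS: 30 − 7 = 23 to 30 + 7 = 37.
- Contact: 23 + 23 = 46 to 37 + 37 = 74.
- AE collection after EOS: 23 to 37 days. If the device is removed at EOS, as 8.3 implies by requiring removal at study completion, this is also the collection time after removal.

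**An early stopper**, taking day 14 after the last dose as an illustration:

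| Sections followed | EOS | Safety contact |
|---|---|---|
| 8.3 second sentence and 8.4 | day 14 | day 14 |
| 8.3 second sentence and 4.1 | day 14 | 14 + 23 = 37 to 14 + 37 = 51 |
| 8.3 first sentence and 4.1 | day 23 to 37 | day 46 to 74 |
| 8.3 first sentence and 8.4 | day 23 to 37 | day 14 |

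The same patient can have the final contact on day 14, on days 37 to 51, or on days 46 to 74, each supported by the text. In the last row the contact comes 23 − 14 = 9 to 37 − 14 = 23 days before the EOS procedures it is meant to follow. The EOS list has its own AE assessment, but 7.21.1 would already have closed monitoring.

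**Position of device removal.** Under 4.1, removal belongs to the EOS procedures and the call comes 23 to 37 days later. Under 8.4 the contact is on the day of stopping. Removal is then at best on the same day, or later if it is still to be scheduled as 7.23 says. No planned contact follows it.

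**What other routes cover after an 8.4 contact.**
- AEs present at withdrawal: re-evaluated within 30 days (7.23).
- Ongoing SAEs: followed to resolution (7.23).
- New SAEs: recorded from consent onwards with no stated end (7.21.3.1), but no scheduled contact elicits them.
- New non-serious AEs: reported only if the investigator thinks it necessary and contacts the sponsor (7.21.1).

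**Scale.** One patient of at most 12 is 1/12 = 8.3%, and more if fewer enroll.

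**The earliest-of rule.** Read literally, 7.21.1 stops monitoring at the contact even when an event is still open. Section 7.23 requires ongoing SAEs at withdrawal to be followed until they resolve. Both cannot be applied as written.

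**The case against.** The best defense is grammatical. Section 7.23 says that, when a patient discontinues, the patient will be asked to take part in the EOS and safety follow-up evaluations. There the time attaches to the asking, not to the call. If 8.4 is read the same way, early stoppers have EOS 30 (±7) days after the last dose and the call 30 (±7) days after that, following a removal that 4.1 places within EOS, and the contradiction over the contact disappears.

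That reading is possible, but two things weigh against it. Section 8.4 sets early stoppers directly against completers, whose visit is timed by interval. Section 7.23 itself asks for AEs only up to the point of discontinuation. The two EOS times in 8.3 raise the same ambiguity. A site cannot be expected to choose the benign reading unaided.

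Other parts of the defense stand. The routes for existing AEs and for SAEs are real, so a reader who inferred that nothing at all is collected from early stoppers after the final visit would go too far. A failed or infected device is replaced so that the patient can stay in the study, so device failure alone is not a planned reason for stopping. On the earliest-of rule, 7.23 is the more specific text for ongoing SAEs and would probably prevail.

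A reader might also infer that device-removal complications are lost through the on-treatment definition in Section 10.6.1.1: "Adverse events that occur up to 30 days after the last dose of study drug will be considered" on-treatment, while EOS falls on days 23 to 37. The documents do not support that. No table is said to be restricted to on-treatment events, AE summaries use all AEs recorded from Study Day 1, and device-related AEs have their own summary with no 30-day limit.

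**Conclusion.** The point holds as an internal contradiction about when AE collection ends for early stoppers. A site following 8.4, 7.21.1 and 7.23 has no planned contact to capture new AEs after device removal, against 23 to 37 days after EOS for completers. The exposed events are chiefly new non-serious ones; new SAEs are reportable but not actively elicited.

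A reader might infer that completers' device-removal events are missed too. They are not, since their collection runs to day 46 to 74. Nor is it shown that the primary endpoint is understated: the size of any loss depends on how many patients stop early and which sections their site follows, and the documents give neither.

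The conclusion assumes that 8.4 times the contact and not merely the invitation, and that removal takes place on or after the day of stopping. It concerns the original protocol and Amendment 1, whose wording on this point is the same. The cover lists Amendments 2 to 8, which are not shown, so whether the wording persists cannot be checked.

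**What to change.** Reconcile Sections 8.3, 8.4, 7.21.1 and 7.23 with Section 4.1 and Appendix 1.

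1. State one rule for the AE-collection contact, for completers and early stoppers alike: the interval 4.1 already gives, counted from the last study procedure, device removal included.
2. Give early stoppers a single EOS time in 8.3, and state in 7.23 and 8.3 how device removal relates to it. Which timing is right is for the sponsor and investigators to settle.
3. Word 8.4 so that it is clear whether the moment of discontinuation governs the request or the contact.
4. Reword the earliest-of rule in 7.21.1 so that it does not close follow-up of SAEs that 7.23 requires to be followed to resolution.

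The cost is protocol wording and one telephone call per early stopper, which 4.1 already promises. Because 8.4 makes participation voluntary for patients who elect to discontinue, the change secures a planned contact but cannot guarantee that each one takes place. If a later amendment has already aligned these sections, confirming that is enough.

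### Sections 8.3, 8.4 and 4.1 conflict on when children who discontinue have their last safety contact, so scheduled AE collection can end inside the protocol's own 30-day on-treatment window

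*Protocol*

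**What the plan says.** The references are to Amendment 1; the original protocol has the same wording in 7.23, 8.3 and 8.4.

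Passages that tie the last assessments of a discontinuing child to the moment of stopping:

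- Section 8.4, on the telephone safety follow-up: patients who discontinue or are withdrawn "will be asked to participate in the safety follow-up visit at the time of discontinuation".
- Section 8.3, second sentence: they "will be asked to participate in the end of study procedures at time of discontinuation".
- Section 7.23: "At the time of discontinuation or withdrawal, patients will be asked to participate in all safety and efficacy evaluations required" for both the EOS visit and the safety follow-up visit.

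Passages that give discontinuers the same timing as completers:

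- Section 8.3, first sentence: "Patients who complete the study or who discontinue prior to the end of the study, will have EOS assessments performed 30" (±7) days after the last dose.
- Section 4.1: EOS for all patients at 30 (±7) days after the last dose, and then "All patients will be contacted by telephone for a Final Safety Follow-up" 30 (±7) days after EOS. The synopsis agrees.
- Appendix 1, footnote h: the call comes 30 (±7) days after EOS. Footnote f, on EOS timing, mentions only patients who complete.

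Two further rules give the conflict its consequence. Section 7.21.1 monitors AEs "until the safety follow-up contact or until the event has resolved or stabilized", or an outcome is reached, whichever is earliest. Section 10.6.1.1 classes as on-treatment "Adverse events that occur up to 30 days after the last dose of study drug".

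**The concern.** Long-term safety is the primary endpoint, and AEs are to be reported as numbers and percentages of patients by dose group. If discontinuers' last scheduled contact falls on the day they stop while completers are followed for about two months after the last dose, those percentages mix unequal observation periods. The shorter period would fall on children who left early. The removal reasons in 7.23 include adverse events, CSF leukocytosis, new seizures, anaphylaxis and refractory spinal fluid leakage, so leaving early may itself be related to harm.

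Discontinuers' EOS laboratory, biomarker and neurodevelopmental values would also be taken at a different time since the last dose than completers' values. At most 12 patients are planned, so one discontinuer is at least 1/12, or about 8%, of the safety population.

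**Working it through.** The protocol states no total follow-up time after the last dose, so there is no figure to reproduce. It follows from the stated windows.

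**Inputs.** EOS at 30 ± 7 days after the last dose (4.1; 8.3, first sentence). Call at 30 ± 7 days after EOS (4.1; footnote h). Section 8.4 gives completers 30 ± 7 days without saying from what, so the anchor has to come from 4.1 or footnote h. On-treatment window 30 days (10.6.1.1). Dosing interval 28 ± 7 days in Groups 1 and 2, and 14 ± 3 days in Group 3 (6.3).

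**Completers.** EOS falls between 30 − 7 = 23 and 30 + 7 = 37 days after the last dose. The call falls between 23 + 23 = 46 and 37 + 37 = 74 days, nominally 30 + 30 = 60.

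**Discontinuers, following 8.4.** Let g be the days from the last dose to discontinuation. The last scheduled contact is on day g. The protocol does not give g. I assume that the child stops before the next dose is overdue, so g runs from 0 to 28 + 7 = 35 in Groups 1 and 2, and from 0 to 14 + 3 = 17 in Group 3.

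- On-treatment days left after the last scheduled contact: max(0, 30 − g).
- Shortfall against completers: 46 − g to 74 − g days.

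| g (days) | On-treatment days without scheduled contact | Shortfall against completers (days) |
|---|---|---|
| 0 | 30 | 46 to 74 |
| 14 | 16 | 32 to 60 |
| 17 | 13 | 29 to 57 |
| 28 | 2 | 18 to 46 |
| 35 | 0 | 11 to 39 |

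The longest g in Group 3 is 17, so under the assumption at least 30 − 17 = 13 on-treatment days are uncovered there. In Groups 1 and 2 the number runs from 30 down to none.

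**Discontinuers, following 8.3 first sentence and 4.1.** EOS on days 23 to 37, call on days 46 to 74. The shortfall is zero and the 30-day window is fully covered.

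The size of the problem therefore depends on which instruction a site follows.

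**The case against.** A reader might infer that AE collection simply closes for every discontinuer on the day of stopping, and that nobody collects what happens next. The documents do not support that.

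- The first sentence of 8.3 and section 4.1 give discontinuers the completers' schedule. The short window is one of two conflicting instructions, not the rule.
- In 7.23 the time phrase can be read as fixing when the family is asked, with the two visits still to come in their usual windows. The same reading is possible in 8.3 and 8.4, though less natural in 8.4.
- Several provisions reach past the last contact. Section 7.23 re-evaluates within 30 days a child who has AEs at withdrawal, follows ongoing SAEs to resolution, and asks for reasonable efforts to monitor AEs after refusal of treatment. Section 7.21.1 lets the investigator raise a late AE with the sponsor. Section 7.21.3.1 requires any SAE after consent to be recorded and gives no end date.

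These points stand, and they also soften the worry about children who stop because of harm, since those children are likely to have an AE present and so to be re-evaluated. They do not remove the gap. The first two provisions in 7.23 concern events already present, the third covers refusal only, and the other two depend on an event coming to light unprompted. None schedules a contact for new events.

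It is also tempting to say that collection closes before the intrathecal device (IDDD) is removed. That order is not established: 4.1 makes removal part of the EOS procedures, while 7.23 says only that it will be scheduled. Nor can one discontinuer be expressed as a share of a dose group, because the protocol gives no group sizes.

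**Conclusion.** The contradiction is real and bears on the primary endpoint. Section 8.4 and the second sentence of 8.3, and on one reading 7.23, conflict with the first sentence of 8.3, with 4.1 and with footnote h. Through 7.21.1, a site following 8.4 can end scheduled collection of new AEs on the day the child stops.

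The size rests on the assumption that the child stops within a permitted dosing interval. A child who has already missed a dose would have a longer gap and a smaller loss; a monthly-dosed child who stops on day 28 loses 2 on-treatment days. What remains uncovered is mainly new events, chiefly non-serious ones, in children with no AE at withdrawal. Participation after discontinuation is voluntary, so some loss would persist under any wording.

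The cover lists Amendments 2 to 8, whose text is not in the part available here. Whether this wording survived could not be checked.

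**What to change.** Reconcile 8.3, 8.4 and 7.23 with the timing already stated in the first sentence of 8.3, in 4.1 and in footnote h. Every child who discontinues would then have, if the family agrees, EOS at 30 (±7) days after the last dose and the AE telephone contact 30 (±7) days after EOS. If the family declines the EOS visit, keep the call on the same timeline, 46 to 74 days after the last dose. State the anchor for the 30 (±7) days in 8.4, and have footnote f cover discontinuers as well as completers. In 7.23, separate when the family is asked from when the visits take place.

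Sections 4.1, 7.23 and 8.3 must also be reconciled on when the IDDD is removed relative to EOS and the final contact.

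The cost is wording in these sections and footnote f, and one telephone call per discontinuer.
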